### 6.2 **Product Complaint**

#### 6.2.1 Definition

A Product Complaint is any Complaint (see Section 6.0 for the definition) related to the biologic or drug component of the product.

For a product this may include, but is not limited to, damaged/broken product or packaging, product appearance whose color/markings do not match the labeling, labeling discrepancies/inadequacies in the labeling/instructions (example: printing illegible), missing components/product, or packaging issues.

[figure not shown]
Any information available to help in the determination of causality to the events outlined directly above should be captured.

### 6.2.2 Reporting

Product Complaints concerning the investigational product must be reported to the Sponsor within 24 hours of the study site's knowledge of the event via the Product Complaint eCRF. Product Complaints occurring during the study will be followed-up to a satisfactory conclusion. All follow-up information is to be reported to the Sponsor (or an authorized representative) and documented in source as required by the Sponsor. Product Complaints associated with adverse events will be reported in the study summary. All other complaints will be monitored on an ongoing basis.

Product Complaints may require return of the product with the alleged complaint condition. In instances where a return is requested, every effort should be made by the investigator to return the product within 30 days. If returns cannot be accommodated within 30 days, the site will need to provide justification and an estimated date of return.

The description of the complaint is important for AbbVie in order to enable AbbVie to investigate and determine if any corrective actions are required.

# 8.0 Statistical Methods and Determination of Sample Size

### 8.1 Statistical and Analytical Plans

This section describes the planned statistical analyses to be performed using data captured according to this protocol. A complete statistical analysis plan (SAP) describing in more detail all planned analyses will be finalized prior to database lock.

The primary endpoints of OS and progress free survival (PFS) assessed by a Central Radiographic Assessment Committee (CRAC) according to RECIST v1.1 in DLL3high patients will be analyzed at the same time after observing at least 319 OS events. It is expected at approximately 420 PFS events will be observed at the time of the primary analysis.

The following analysis sets are considered:

- **DLL3**high **Set:** It includes all randomized subjects with DLL3high ED SCLC. Subjects will be classified according to the treatment arm to which they are randomized regardless the actual treatment received, following intent-to-treat principle. The DLL3high set will be the analysis set for the analysis of the primary efficacy endpoints of OS and PFS. All the exploratory efficacy endpoints will be analyzed based on the DLL3high set unless the OS and PFS based on the randomized set are statistically significant.
- Randomized Set: It includes all randomized subjects, with subjects grouped according to the treatment arm to which they are randomized regardless the actual treatment received, following intent-to-treat principle. The randomized set will be the analysis set for key secondary efficacy endpoints of OS and PFS, and key secondary endpoint of EORTC QLQ-C30 physical functioning domain. All the exploratory efficacy endpoints will be analyzed based on the randomization set if the OS and PFS based on the randomization set are statistically significant.
- **Per Protocol Set:** It includes all subjects in the randomized set without any major protocol violations which may affect the evaluation of the primary

efficacy endpoint. Major protocol violations will be defined in the SAP prior to the database lock. Subjects will be classified according to treatment assigned at the time of randomization. The per protocol set will be used for supportive analysis of efficacy endpoints.

- **Safety Set:** It includes all subjects who received at least one dose of study drug and subjects will be classified according to treatment received. Thus a subject who is randomized to the rovalpituzumab tesirine arm but does not receive rovalpituzumab tesirine will be considered in the placebo arm for safety analysis. Dexamethasone treatment will not be taken into consideration for subjects' classification in the Safety set.
- Pharmacokinetic-Evaluable Set: It consists of all subjects who receive at least one dose of study drug, with subjects classified according to the actual treatment received. A baseline measurement and at least one blood sample following a dose of study treatment is required for inclusion in this analysis.

### 8.1.1 **Disposition of Study Subjects**

[figure not shown]
The disposition of subjects will be summarized by treatment arm in the randomized set. The subject disposition includes the number of subjects for whom study drug was permanently discontinued (including the reasons for discontinuation), and the number of subjects who discontinued early from the study.

### **Demographics and Baseline Characteristics** 8.1.2

Demographic and baseline characteristics will be summarized in the DLL3high set and randomized set.

### 8.1.3 **Efficacy Endpoints and Analyses**

Assessment of response and progression will be determined by the CRAC according to RECIST v1.1.

# 8.1.4 Primary Efficacy Endpoints

[figure not shown]
Progression-free survival (PFS) and overall survival (OS) in subjects with DLL3high ED SCLC are the two primary efficacy endpoints.

PFS will be defined as the number of months from randomization to disease progression, as assessed by the CRAC per RECIST v1.1, or death of any cause, whichever occurs first. Disease progression and censoring rules will be based on published conventions.  If a subject neither experienced disease progression nor died, then the data will be censored at the last date of post-baseline radiographic assessment. If a subject with no post-baseline assessment did not experience disease progression nor died, then the data will be censored at the date of randomization.

Differences between the treatment arm and the placebo arm in PFS will be assessed by a log-rank test stratified by the randomization stratification factors, testing the null hypothesis (rovalpituzumab tesirine arm is not superior to placebo arm in PFS). The hazard ratios of the treatment arm over the placebo arm will be calculated by a Cox's proportional hazards regression model adjusting for the main-effects of the stratification factors. Median PFS and 95% confidence intervals will be estimated using Kaplan-Meier survival methodology, with the Kaplan-Meier survival curves presented to provide a visual description. PFS rates at 3, 6, 9, and 12 months after randomization with 95% confidence intervals will be reported. Estimates of the treatment effect will be expressed as hazard ratio including 95% confidence intervals estimated through a Cox proportional-hazards regression model adjusting for the main-effects of the stratification factors.

Overall survival will be defined as the number of months from randomization to death of any cause. OS and censoring rules will be based on published conventions. If a subject has not died, the data will be censored at the last date documented to be alive.

Differences between the treatment arm and the placebo arm in OS will be assessed by a log-rank test stratified by the randomization stratification factors, testing the null hypothesis (rovalpituzumab tesirine arm is not superior to placebo arm in OS). The

hazard ratios of the treatment arm over the placebo arm will be calculated by a Cox's proportional hazards regression model adjusting for the main-effects of the stratification factors. Median OS and 95% confidence intervals will be estimated using Kaplan-Meier survival methodology, with the Kaplan-Meier survival curves presented to provide a visual description. OS rate at 6, 12, 18, and 24 months and corresponding 95% confidence intervals will be reported. Estimates of the treatment effect on will be expressed as hazard ratio including 95% confidence intervals estimated through Cox proportional-hazards regression models adjusting for the main-effects of the stratification factors.

# 8.1.5 Secondary Efficacy Endpoints

The secondary efficacy endpoints in the randomized set are:

[figure not shown]
- OS
- PFS per the CRAC based on RECIST v1.1
- EORTC QLQ-C30 physical functioning domain

Secondary time-to-event endpoints (PFS and OS) will be analyzed using the similar statistical methods described for the primary endpoints.

# 8.1.6 Exploratory Efficacy Endpoints

The exploratory efficacy endpoints in both DLL3high and randomization set are:

- Objective response rate (ORR) per the CRAC based on RECIST v1.1
- PFS per investigator assessment based on RECIST v1.1
- ORR per investigator assessment based on RECIST v1.1
- Clinical benefit rate (CBR) per the CRAC and investigator assessment, respectively, based on RECIST v1.1
- Duration of response (DOR) per CRAC and investigator assessment, respectively

 Change from baseline in all PRO domains (except physical functioning) measured by EORTC QLQ-C30/LC13 and EQ-5D-5L

ORR is defined as the proportion of patients with a best overall response (BOR) of confirmed complete response (CR) or partial response (PR) by CRAC review according to RECIST v1.1.

[figure not shown]
CBR is defined as the proportion of patients with a BOR of CR or PR, or SD by CRAC review according to RECIST v1.1.

ORR and CBR in treatment arms will be compared using Cochran-Mantel-Haenszel test stratified by randomization stratification factors. Rates and 95% confidence intervals will be reported for each treatment arm.

The duration of overall response for a given subject will be defined as the number of months from the day the criteria are met for confirmed complete response (CR) or partial response (PR) by CRAC (whichever is recorded first) to the date of progressive disease or death, whichever comes first. If a subject is still responding (i.e., has not progressed nor died after CR or PR), then the subject's data will be censored at date of the last radiographic assessment by CRAC. For subjects who never experienced CR or PR, these subjects' data will not be included in the duration of response analysis. Distribution of the duration of response will be estimated for each treatment arm using Kaplan-Meier methodology. Median duration of overall response with corresponding 95% CI for each treatment arm will be provided.

# 8.1.7 Patient Reported Outcomes (PRO)

The EORTC QLQ-C30/LC13 scoring manual will be used to transform the raw scores into the domain scores (global heath, functional scales, symptom scales/items). Physical functioning scale score in EORTC QLQ-C30 is the key secondary endpoint. Change from baseline of the items and domains of the QLQ-C30/LC13 will be summarized by treatment arm. The EQ-5D-5L manual and the published weights will be used to convert the individual items to the utility scores. Change from baseline of the EQ-5D-5L utility

score and VAS will be summarized by treatment arm. The treatment group differences will be evaluated by analyzing the change from baseline using a one-way analysis of variance (ANOVA) model.

# 8.1.8 Planned Sensitivity and Subgroup Analyses

Efficacy analyses for the primary endpoints (PFS per CRAC and OS) will be performed in the per-protocol set.

[figure not shown]
In the DLL3high and randomized sets, treatment effects for the primary endpoints (PFS per CRAC and OS) will be assessed in the following subgroups:

- RECIST v1.1 response after completion of first-line platinum-based therapy at screening assessment (SD vs. PR/CR)
- DLL3 expression (Unknown vs. 0% to < 25% vs. 25% to < 75% vs. 75% or above) for the randomized set only
- History of CNS metastases (Yes vs. No)
- For subjects with no history of CNS metastases, PCI vs. No PCI
- Lactate dehydrogenase (LDH), ≤ ULN vs. > ULN
- Number of metastatic sites, 0 1 vs. > 1
- Age group (age < 40 vs. 40 to < 60 vs. 60 or older)
- Gender
- Race
- ECOG (0 vs. 1)

Differences between rovalpituzumab tesirine arm and the placebo arm for time-to-event endpoints will be assessed by an unstratified log-rank test for each subgroup. Hazard ratios of treatment arm over the placebo arm will be calculated by a Cox's model.

# 8.1.9 Pharmacokinetic and Exposure-Response Analyses

Serum concentrations of rovalpituzumab tesirine ADC as well as the incidence and timing of ATA formation will be tabulated and summary statistics will be computed. Serum

concentration and ATA data from this study may be combined with data from other studies and analyzed using population pharmacokinetic methodologies.

The relationship between pharmacokinetics (e.g., exposure) and clinical trial findings including, but not limited to demographics, efficacy, and/or safety measures may also be explored. Additional analyses will be performed if useful. Results of the population pharmacokinetic and exposure-response analyses will be provided in a separate report.

# 8.2 Safety Analyses

Safety endpoints will be summarized using data from the Safety set. Safety analyses will involve examination of the incidence, severity, and type of treatment-emergent adverse events (TEAEs) reported, changes in vital signs and laboratory test results from baseline (the assessment prior to first dose) to specified time points throughout the study, and concomitant medications used. NCI CTCAE version 4.0 will be used in the grading of adverse events and laboratory abnormalities that are reported as adverse events.

# 8.2.1 Treatment-Emergent Adverse Events (TEAEs)

[figure not shown]
TEAEs reported during the study will be coded using a MedDRA dictionary. Incidence of TEAEs will be summarized by treatment arm and the following:

- System organ class and preferred term
- System organ class, preferred term, and severity

These summaries will be presented for the following subsets:

- Serious TEAEs
- All TEAEs
- Drug-related TEAEs

For tables reporting AEs by severity, if a subject has multiple occurrences of an AE with the same organ class and preferred term, the most severe event will be presented.

### 8.2.2 Clinical Laboratory Evaluation

Laboratory parameters will be summarized by treatment arm at each visit. Each summary will include the values of the laboratory parameters and changes from baseline. Shift tables from baseline will be presented for laboratory values in the chemistry and hematology panels. Parameters will be classified according to the laboratory reference normal ranges. A listing will be provided for out-of-normal range as well as clinically significant abnormal lab values.

# 8.2.3 Vital Signs

Vital signs including pulse, blood pressure, temperature, and body weight will be summarized by treatment arm and time point. For each assessment of vital signs, change from baseline will be summarized by treatment arm.

### 8.2.4 ECOG Performance Status

ECOG performance status will be summarized for each visit by treatment arm. Shifts from baseline to the best and worst post-baseline score may be tabulated.

# 8.2.5 Electrocardiogram

[figure not shown]
ECG status will be summarized for each scheduled visit by treatment arm. Shifts from baseline may be tabulated.

### 8.2.6 Concomitant Medications

Concomitant medications will be classified according to the anatomical therapeutic chemical (ATC) codes in the World Health Organization Drug (WHODRUG) dictionary. The incidence rate of each coded concomitant medication will be tabulated by treatment arm. The table will be sorted by the incidence use of the entire sample.

# 8.3 Type I Error Adjustment Procedure for Multiple Testing

To meet global regulatory requirements, a multiple testing strategy will be implemented to control the family-wise type I error (alpha) to one-sided 0.025 level for comparisons of

rovalpituzumab tesirine arm versus placebo arm with respect to progression-free survival (PFS) per CRAC in DLL3high set, overall survival (OS) in DLL3high set, PFS per CRAC in randomized set, OS in randomized set, and physical functioning scale score (EORTC QLQ-C30) in randomized set.

The following null hypotheses are considered:

Two hypotheses in  $H_{01}$  are  $H_{01a}$  and  $H_{01b}$ .

 $H_{01a}$ : Rovalpituzumab tesirine arm is not superior to placebo arm in PFS per CRAC in DLL3high set.

[figure not shown]
H01b: Rovalpituzumab tesirine arm is not superior to placebo arm in OS in DLL3high set.

H02: Rovalpituzumab tesirine arm is not superior to placebo arm in OS in randomized set.

H03: Rovalpituzumab tesirine arm is not superior to placebo arm in PFS per CRAC in randomized set.

H04: Rovalpituzumab tesirine arm is not superior to placebo arm in physical functioning scale score (EORTC QLQ-C30) in randomized set.

The null hypotheses will be tested in a fixed sequence of  $\{H_{01a}, H_{01b}, H_{02}, H_{03}, \text{ and } H_{04}\}$  in order. To maintain the family-wise type I error for the study, the null hypotheses in  $H_{01}$  ( $H_{01a}$  and  $H_{01b}$ ) will be first tested with an alpha-split approach. The one-sided alpha of 0.25% and 2.25% will be assigned for PFS and OS hypothesis in  $H_{01}$ , respectively. Out of one-sided alpha of 2.25% allocated to OS hypothesis ( $H_{01b}$ ), the one-sided alpha of  $10^{-6}$  will be spent for the early look at the OS data for futility analysis. If the hypothesis for PFS in  $H_{01}$  ( $H_{01a}$ ) is rejected the one-sided alpha of 0.25% will be recycled to the OS hypothesis in  $H_{01}$  ( $H_{01b}$ ). Hence, the hypothesis for OS in  $H_{01}$  ( $H_{01b}$ ) will be tested either at a one-sided 2.4999% or one-sided 2.2499% level of significance depending on the PFS hypothesis in  $H_{01a}$  is rejected or not.

[figure not shown]
Rovalpituzumab Tesirine M16-298 Protocol Amendment 4 EudraCT 2016-003503-64

[figure not shown]
If either PFS or OS endpoint reaches statistical significance, the study is considered positive. No further tests will be performed if the OS endpoint in DLL3high population  $(H_{01b})$  does not reach statistical significance.

The hypothesis in  $H_{02}$  will be tested if the hypothesis in  $H_{01b}$  is rejected. If the hypothesis in  $H_{02}$  is rejected, then, either (i)  $H_{03}$  and  $H_{04}$  will be tested sequentially if the PFS endpoint in DLL3high subjects ( $H_{01a}$ ) is also rejected or (ii) only  $H_{04}$  will be tested if the PFS endpoint in DLL3high subjects ( $H_{01a}$ ) is not rejected.

Diagram of Hierarchical Testing of Primary and Secondary Endpoints is described in Figure 3.

Figure 3. Diagram of Hierarchical Testing of Primary and Secondary Endpoints

[figure not shown]
### 8.4 Determination of Sample Size

There are two primary efficacy endpoints for this study: Progression-free survival (PFS) based on the CRAC and overall survival (OS) in DLL3high ED SCLC patients. To maintain the overall 1-sided type I error at a 2.5% for this study, the type I error will be split, assigning 0.25% to progression-free survival and the remaining 2.25% to overall survival. However, the OS endpoint will be tested at a one-sided 2.2499% significance level as a one-sided alpha of  $10^{-6}$  will be spent for the early look at the OS data for futility analysis.

The sample size of the study is primarily determined by the analysis of OS. It is assumed, taking into account the expected patient population for the study, that median overall survival in the placebo and rovalpituzumab tesirine arm will be around 9 months and 13 months, respectively. The increase of median OS in rovalpituzumab tesirine arm corresponds to a hazard ratio of 0.69, i.e., a reduction in the hazard of death by 31%. With all these assumptions, a total of 319 deaths among subjects with DLL3high are needed to achieve a 90% power based on a log-rank test at a one-sided significance level of 0.022499. Assuming a 19-month accrual period and the last enrolled subject followed for 12 months, at least 480 subjects with DLL3high are expected to be randomized (240 subjects in each arm). A total of 740 subjects regardless of DLL3 expression level (including 480 subjects with DLL3high) will enroll in the study, assuming an approximate prevalence of 65% for subjects with DLL3high. For one-sided significance level of 0.022499, it is projected that an observed hazard ratio of 0.799 or less, corresponding to a 2.3 months or greater improvement in median OS, would result in a statistically significant improvement in the primary analysis of OS.

The primary endpoints of OS and PFS in DLL3high patients will be analyzed at the same time after observing at-least 319 OS event. It is expected at approximately 420 PFS events will be observed at the time of the primary analysis.

It is assumed, taking into account the expected patient population for the study, that median progression-free survival for the placebo and rovalpituzumab tesirine arm will be

approximately 3 months and 4.5 months, respectively. The increase of median progression-free survival in rovalpituzumab tesirine arm corresponds to a hazard ratio of 0.667. With all these assumptions, a total of approximately 420 PFS events assessed by the CRAC for the subjects with DLL3high are needed to achieve a 91% power based on a log-rank test at a one-sided significance level of 0.0025. It is projected that an observed hazard ratio of 0.760 or less, corresponding to approximately 1 month or greater improvement in median PFS, would result in a statistically significant improvement in the PFS.

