## **Futility Analysis:**

Unblinded interim data will be analyzed and reviewed by the IDMC. A futility analysis will be conducted when approximately 160 deaths in subjects with DLL3 high ED SCLC (approximately 50% of the planned deaths) are observed. The trial may be stopped for futility if the estimated Overall Survival Cox HR of Rova-T to Placebo at this analysis exceeds 0.9. The one-sided alpha of 10^-6 will be spent for the early look at the efficacy data for futility analysis.

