4.4 Sample Size

There are two primary efficacy endpoints for this study: Progression-free survival (PFS) based on the CRAC and overall survival (OS) in DLL3^{high} ED SCLC subjects. To maintain the overall 1-sided type I error rate at a 2.5% for this study, the type I error will be split, assigning 0.25% to progression-free survival and the remaining 2.25% to overall survival. However, the OS endpoint will be tested as a one-sided 2.2499% significance level as a one-sided alpha of 10^{-6} will be spent for the early look at the OS data for futility analysis.

Sample size of the study is primarily determined by the analysis of OS. It is assumed, taking into account the expected patient population for the study, that median overall survival in the placebo and rovalpituzumab tesirine arm will be around 9 months and 13 months, respectively. The increase of median OS in rovalpituzumab tesirine arm corresponds to a hazard ratio of 0.69, i.e., a reduction in the hazard of death by 31%. With all these assumptions, a total of 319 deaths among subjects with DLL3^{high} are needed to achieve 90% power based on a log-rank test at a one-sided significance level of 0.022499. Assuming a 19-month accrual period and the last enrolled subject followed for 12 months, at least 480 subjects with DLL3^{high} are expected to be randomized (240 subjects in each arm). A total of 740 subjects regardless of DLL3 expression level (including 480 subjects with DLL3^{high}) will enroll in the study, assuming an approximate prevalence of 65% for subjects with DLL3^{high}.

The primary endpoints of OS and PFS will be analyzed at the same time after observing at least 319 OS events in subjects with DLL3^{high}. It is expected that approximately 420 PFS events assessed by the CRAC will be observed at the time of the primary analysis.

It is assumed, taking into account the expected patient population for the study, that median progression-free survival for the placebo and rovalpituzumab tesirine arm will be approximately 3 months and 4.5 months, respectively. The increase of median progression-free survival in rovalpituzumab tesirine arm corresponds to a hazard ratio of 0.667. With all these assumptions, a total of approximately 420 PFS events assessed by the CRAC for the subjects with DLL3^{high} are needed to achieve 91% power based on a log-rank test at a one-sided significance level of 0.0025.

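### The stated 90% OS and 91% PFS power are single-look figures; if the HR > 0.9 futility rule is followed, power is about 88% for OS and about 87–89% for PFS

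*Protocol*

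**What the plan says.** For OS, protocol 8.4 assumes medians of 9 and 13 months, which "corresponds to a hazard ratio of 0.69, i.e., a reduction in the hazard of death by 31"%. It concludes that "a total of 319 deaths among subjects with" DLL3-high tumours "are needed to achieve a 90% power based on a log-rank test at a one-sided significance level of 0.022499". For PFS, about 420 CRAC-assessed events at HR 0.667 "are needed to achieve a 91% power based on a log-rank test at a one-sided significance level of 0.0025". The Synopsis repeats these statements, and SAP 4.4 says the same of OS: "are needed to achieve 90% power based on a log-rank test at a one-sided significance level of 0.022499". OS and PFS are analysed at the same time, after at least 319 deaths (protocol 8.1 and 8.4, SAP 4.4).

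The futility look is at about 160 DLL3-high deaths, roughly half of those planned. The Synopsis states: "The trial may be stopped for futility if the estimated Overall Survival Cox HR of Rova-T to Placebo at this analysis exceeds 0.9". Protocol 8.5 and SAP 4.6.1 repeat the rule. They make any stop depend on an IDMC recommendation that also weighs other efficacy and safety data, and they leave details to the IDMC charter. Section 1.1 records that this amendment added the look. The sample-size sections allow for it only by lowering the OS alpha from 0.0225 to 0.022499.

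**The concern.** A futility look leaves the type I error intact but costs power, because some trials that would have succeeded are stopped. Reducing alpha by 10^-6 does not capture that cost. Neither document gives the power with the rule applied or the chance of stopping when the assumed effect is real.

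The PFS consequence is the less obvious one. PFS has its own alpha, and either endpoint alone makes the study positive (protocol 8.3). Yet PFS is tested only at the final OS analysis, so an OS-based stop also removes the planned PFS test. A reader of 8.4 would take 90% and 91% as properties of the design as it will be run.

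**Working it through.** **Inputs.** From protocol 8.3–8.5:
- OS HR 9/13 = 0.6923, rounded in the text to 0.69; 319 deaths; one-sided alpha 0.022499 (z = 2.0047)
- PFS HR 0.667; 420 events; one-sided alpha 0.0025 (z = 2.8070)
- 1:1 allocation
- futility look at 160 deaths, stop if HR > 0.9

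**Step 1: reproduce the plan's figures (one look, no stop).** Use Z ~ N(|ln HR|·√D/2, 1).
- Deaths for 90% OS power: 4(2.0047 + 1.2816)²/0.3677² = 319.5. At alpha 0.0225 the answer is the same to one decimal, so the 10^-6 spend has no visible effect.
- OS power with 319 deaths: Φ(0.3677·√319/2 − 2.0047) = Φ(3.284 − 2.005) = 90.0%. At HR 0.69 it is 90.5%.
- PFS power with 420 events: Φ(0.4050·√420/2 − 2.8070) = Φ(4.150 − 2.807) = 91.0%.
- Critical hazard ratios: 0.799 and 0.760, as stated.

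The stated powers therefore reproduce without any futility term.

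**Step 2: chance of stopping under the design effect.** On the Z scale, HR 0.9 at 160 deaths is 0.10536·√160/2 = 0.666. The mean of the interim Z is 0.3677·√160/2 = 2.326. P(stop) = Φ(0.666 − 2.326) = 4.9% at HR 9/13, and 4.6% at HR 0.69.

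**Step 3: power with the rule followed.** This is the bivariate normal probability of continuing and then rejecting. For OS the interim–final correlation is √(160/319) = 0.708. For PFS, the correlation r between the interim OS and final PFS statistics is not in the documents, so it is varied. The PFS rows take OS HR 9/13.

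| | No stop | Rule followed |
|---|---|---|
| OS, HR 9/13, alpha 0.022499 | 90.0% | 88.0% |
| OS, HR 0.69, alpha 0.022499 | 90.5% | 88.6% |
| OS, HR 9/13, alpha 0.024999 throughout | 90.7% | 88.7% |
| PFS, r = 0 | 91.0% | 86.6% |
| PFS, r = 0.3 | 91.0% | 87.3% |
| PFS, r = 0.5 | 91.0% | 87.9% |
| PFS, r = 0.7 | 91.0% | 88.9% |

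With OS HR 0.69 the PFS row for r = 0.7 becomes 89.0%. The third row is a ceiling for recycling, since the higher OS alpha applies only when PFS is rejected. Simulating the actual procedure gives about 88.5% at HR 9/13 with the rule followed.

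**Step 4: cross-check.** Patient-level simulation used the protocol's accrual rates and medians and several assumed PFS–OS dependence models (6,000 trials each). The stop probability was 4.6–5.4%, OS power fell from 89.0–90.3% to 87.1–88.4%, and PFS lost 2.9–3.9 points. The interim-OS/final-PFS correlation was 0.37–0.57, inside the range tabulated.

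**The case against.** - **The sentence in 8.4 is true as written.** It describes a log-rank test with a given number of deaths at a given alpha, and the formula gives that answer. This stands: nothing is miscalculated.
- **The rule is permissive.** The trial may be stopped, and only after the IDMC has weighed other evidence. This also stands. The 88% is the value if every crossing leads to a stop and 90% the value if none does. The rule is nevertheless in the plan to be used, and the plan gives only the more favourable end.
- **Alpha recycling is left out of the 90%.** OS "will be tested either at a one-sided 2.4999% or one-sided 2.2499% level of significance", depending on whether PFS is rejected. This narrows the gap to the stated 90% to about 1.5 points at HR 9/13, but does not close it. Recycling raises the no-stop figure as well (90.7% against 88.7% at the ceiling), so the cost of the rule itself is still about 2 points. It gives nothing back to PFS.
- **The charter may report these figures.** It may, and it is not available here. The point is therefore confined to the protocol and SAP, where the power claims are made. One cannot conclude that the IDMC is unaware of the cost.
- **The PFS figure needs an assumption.** It does, which is why a range is given. It also assumes no confirmatory PFS test after a stop, a case the documents do not address.

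**Conclusion.** The point holds as an undisclosed operating characteristic of modest size. With the rule followed, the chance of stopping under the design effect is about 5%. OS power is 88.0–88.6% at alpha 0.022499 (about 88.5% at HR 9/13 with recycling), against a stated 90%. PFS power is about 87–89% for correlations of 0 to 0.7, against a stated 91%. The OS figures are firm; the PFS range is only as good as the assumed correlation. All assume proportional hazards, the normal approximation, a look at 160 deaths, and a stop whenever the estimate exceeds 0.9.

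A reader might infer more than this:
- That the sample size was miscalculated. It was not; every stated figure reproduces.
- That the type I error is affected. It is not, since the alpha is set as though the trial always continues.
- That more deaths are required. The documents do not commit to 90% with the stop enforced, and a shortfall of about 2 points under full adherence does not by itself call for a larger trial.
- That the 0.9 threshold is badly placed. At an interim HR of exactly 0.9, conditional power is 56% if the remaining deaths follow the design effect but 6.6% if the observed trend continues. The choice is a judgement that the documents leave open.

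**What to change.** In the Synopsis, protocol 8.4 and SAP 4.4:
- Label 90% (OS, 319 deaths) and 91% (PFS, 420 events) as power without a futility stop.
- Add the power with the HR > 0.9 rule followed: about 88% for OS, and about 87–89% for PFS with the assumed correlation between interim OS and final PFS stated.
- Add the probability of stopping under the alternative, about 5%.
- Say that a futility stop forgoes the planned PFS test.

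Event counts, alpha allocation and the futility threshold need no change. The cost is a sentence or two in each place, and a stated power that is slightly less favourable.
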